16. Women who are pregnant.

17. Acute illness or active infection at the time of index procedure documented by pain, fever, drainage, positive culture and/or leukocytosis (WBC > 11.000 mm³) for which antibiotics have been or will be prescribed.
18. Creatinine \geq 2.5 mg/dl (or \geq 221 μ mol/L).
19. Unstable angina.
20. Myocardial infarction within the previous 60 days.
21. Left ventricular ejection fraction less than 40%.
22. History of blood clotting or bleeding abnormalities.
23. Contraindication to anticoagulation.
24. Contraindication to computed tomography or magnetic resonance imaging procedures.
25. Life expectancy of less than 1 year.
26. Enrollment in another investigational study.
27. Uncontrolled heart failure (NYHA class III or IV heart failure).
28. Presence of an intramural thrombus, tumor, or other abnormality that precludes catheter introducing or positioning.
29. Presence of a condition that precludes vascular access.
30. Left atrial size \geq 50mm.
31. INR greater than 3.0 within 24 hours of procedure.*
32. Use of amiodarone therapy within the 3 months prior to the ablation procedure

**If subject's INR is minimally >3.0 within 24 hours pre-procedure, another INR may be done on day of procedure, if INR results < 3.0, subject may be enrolled.*

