- Changes in mental status
- Femoral neuropathy
- Nerve injury/peripheral neuropathy
- Vagal nerve injury

Other

- Esophageal injury, e.g. Atrio-esophageal fistula

- Bleeding from anticoagulant medications
- Gastric motility/pyloric spasm
- Headache
- Heparin induced thrombocytopenia (HIT)
- Permanent or temporary nerve damage to the heart or diaphragm
- Renal failure/insufficiency, transient or chronic
- Surgery required for treatment of an adverse event
- Increased exposure to radiation

Subjects will be offered sedation throughout the procedure. General risks of sedation include but are not limited to:

- Allergic reaction
- Aspiration
- Cardiac arrest
- Death
- Low/high blood pressure
- Nausea and/or vomiting
- Respiratory difficulties
- Headache

Clinical evaluation of the Hansen System in humans is justified because the risks are reasonable in relation to the expected benefits of device use.

Other risks potentially associated with the Artisan Extend Catheter include:

- Prolongation of the procedure
- General vessel damage
- Damage to vessels adjacent to the vessels used for advancing the system

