Aneurysm	Localized widening (dilatation) of an artery, vein, or the heart. At the area of an aneurysm, there is typically a bulge and the wall is weakened and may rupture.
Atrio-venous fistula	Formation of an abnormal connection between the lumens of an artery and a vein as documented by CT, ultrasound, angiography, or direct observation.
Access site discomfort	Pain and/or tenderness at the access site.
Bleeding	Bleeding requiring observation resulting in prolonged hospitalization and/or transfusion and/or treatment other than applying pressure & bandage.
Hematoma	A mass of usually clotted blood that forms in tissue, organ or body space as a result of leakage from a blood vessel that requires additional treatment beyond applying pressure.
Retroperitoneal hemorrhage	Bleeding into the retroperitoneal space. RPH is often associated with femoral artery sheath placement superior to the inferior epigastric artery resulting in vessel perforation.
Perforation or rupture of a blood vessel	Defined as perforation in an access vessel wall or the aorta confirmed by extravasations of contrast under fluoroscopy.

C. VASCULAR COMPLICATIONS	DEFINITION
Pseudoaneurysm	Enlargement of the aorta, iliac, or femoral arteries, which contain some or all of the medial layer, the adventitia, and periaortic tissue most commonly associated with previous aortic operative procedures, trauma, and/or infection. Pseudoaneurysms typically present as a well-defined collection of blood outside the vessel wall from contained rupture.
Temporary or total occlusion of an artery	Vessel lumen narrowing or obstruction by atherosclerotic plaque, thrombus, or embolism causing a decrease or occlusion of blood supply to the extremities.
Thrombophlebitis	Inflammation of a vein that occurs when a blood clot forms.
Vessel Spasm	A sudden constriction of a vessel limiting blood flow downstream.
Other Access site complications	Any new or exacerbated significant vascular complication that causes clinically relevant changes in the subject's health for which medical attention is required.

D. NEUROLOGIC COMPLICATIONS	DEFINITION
Change in Mental Status	A delirium or acute confusional state associated with a disturbance in cognition, mood, attention, arousal, and self-awareness, as evidenced on clinical assessment, which arises acutely, either without prior intellectual impairment or superimposed on chronic intellectual impairment.

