Femoral Neuropathy	Pain and numbness in the anterior thigh associated with quadriceps muscle weakness and decreased patellar reflex lasting > 1 month after treatment.
Nerve Injury/Peripheral Neuropathy	Direct damage to nerves surrounding the access site, operative field, and the resultant signs and/or symptoms of such damage.
Other neurologic complications	Any new or exacerbated significant neurologic complication that causes clinically relevant changes in the subject's health for which medical attention is required.

E. OTHER COMPLICATIONS	DEFINITION
Headache	Headache lasting >24 hours and/or not relieved by pain medication.
Heparin induced thrombocytopenia (HIT)	Development of thrombocytopenia (low platelet counts) due to the administration of Heparin. It predisposes to thrombosis, the formation of abnormal blood clots inside a blood vessel.
Renal Insufficiency	Slowly progressive failure of renal function resulting from some disease, e.g., diabetes, cancer, hypertension, glomerulonephritis, that causes gradual destruction of the kidneys, or if creatinine levels are available, an increase of > 25% above the pre-procedure creatinine level.
Renal failure	Defined as a new need for dialysis or a creatinine increasing to 3.5 mg/dL or greater. Not included as Renal Failure is any Renal Dysfunction defined as an increase of creatinine over 1.0 mg/dL over the baseline.
Surgery required for treatment of an Adverse Event	Emergent or Urgent surgery required to treat an adverse event.
Increased exposure to radiation	Radiation exposure resulting in symptoms consistent with overexposure to radiation.
Other possible adverse effects	Any new or exacerbated significant complication that causes clinically relevant changes in the subject's health for which medical attention is required.

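### Appendix A's two sentences defining renal failure contradict each other: no eligible subject can meet the creatinine criterion as written

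*Protocol*

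**What the plan says.** The Renal failure row of Appendix A (part E, Other Complications) has two sentences. The first sets the criteria: "Defined as a new need for dialysis or a creatinine increasing to 3.5 mg/dL or greater". The second takes cases out again: "Not included as Renal Failure is any Renal Dysfunction defined as an increase of creatinine over 1.0 mg/dL over the baseline". Nothing links the two; the second sentence has no qualifier covering a subject who also reaches 3.5 mg/dL or starts dialysis. Renal dysfunction has no row of its own in Appendix A.

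The Renal Insufficiency row of the same table can be met on creatinine alone: "if creatinine levels are available, an increase of > 25% above the pre-procedure creatinine level".

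Exclusion criterion 18 in Section 7.1, repeated in the synopsis, bars subjects at or above 2.5 mg/dL: "Creatinine \geq 2.5 mg/dl".

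The row is meant to be used. Appendix A says its definitions apply to expected adverse events that must be reported, and Section 8.1 lists renal failure and insufficiency among the risks. Creatinine is measured at baseline and before discharge. Under Table 9 it is measured again at 30 days only in subjects with chronic renal failure or a raised value during the index hospitalization.

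**The concern.** An event definition should tell a coder which cases are in and which are out. Here the first sentence admits a subject whose creatinine reaches 3.5 mg/dL, and the second excludes the same subject because the rise exceeds 1.0 mg/dL. Two coders could classify one case differently and both cite the text.

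If the second sentence governs, a subject going from 1.0 to 3.6 mg/dL (a rise of 2.6 mg/dL, or 260%) goes into the same row as one going from 1.0 to 1.3 mg/dL (30%). The row for the more severe event would then contain no creatinine-defined case, whatever happened to the subjects. Adverse events and serious adverse events are reported analyses under Sections 5.5 and 6.7, so a reader of those tables could take an empty row as a clinical result when it follows from the wording.

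**Working it through.** The protocol states no figure to reproduce here. The check compares its thresholds.

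**Inputs**
- Eligible baseline creatinine: b < 2.5 mg/dL (Section 7.1, exclusion 18). The criterion also gives 221 µmol/L. The two units agree: 2.5 × 10,000 / 113.12 = 221.0.
- Renal failure, creatinine criterion: c ≥ 3.5 mg/dL (Appendix A).
- Renal failure, exclusion: c − b > 1.0 mg/dL (Appendix A).
- Renal insufficiency: (c − b)/b > 25% (Appendix A).

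**Step 1: does reaching 3.5 mg/dL always trigger the exclusion?** The smallest qualifying rise is 3.5 − b. With b < 2.5 this exceeds 3.5 − 2.5 = 1.0.

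| Baseline b (mg/dL) | Rise to 3.5, 3.5 − b | Percent rise, (3.5 − b)/b |
|---|---|---|
| 0.6 | 2.9 | 483.3% |
| 1.0 | 2.5 | 250.0% |
| 1.5 | 2.0 | 133.3% |
| 2.0 | 1.5 | 75.0% |
| 2.4 | 1.1 | 45.8% |
| 2.499 | 1.001 | 40.1% |

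The value 1.0 is a limit that no eligible subject attains. Every eligible subject who meets the creatinine criterion is therefore excluded by the next sentence.

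**Step 2: what happens to the dialysis criterion?** It survives in part. New dialysis with a rise of 1.0 mg/dL or less still counts. New dialysis with a rise above 1.0 mg/dL is excluded on the literal reading.

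**Step 3: where do the excluded cases go?** A rise above 1.0 from a baseline below 2.5 is a rise of more than 1.0/2.5 = 40%. That always exceeds the 25% limit, so each case can still be reported as renal insufficiency.

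**Step 4: does limiting the exclusion remove the conflict?** Suppose it applies only to rises above 1.0 mg/dL that stay below 3.5 mg/dL without new dialysis. For b = 1.0, values above 2.0 and below 3.5 are not renal failure, and 3.5 or more is. For b = 2.4, the bands are above 3.4 to below 3.5, and 3.5 or more. No value falls under both sentences.

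**The case against.** The best defence is that the second sentence was meant to say that a rise above 1.0 mg/dL is not enough by itself to be renal failure. That is plausible, and a sensible coder might apply it. But the text does not say so, and it uses a term with no row to which the case could be assigned. So the defence explains the likely intention and leaves the contradiction in place.

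The defence is stronger on consequences, and that part stands. All adverse events are collected from consent (Section 5.2). Seriousness is judged on outcome criteria in Section 7.8.2 and does not depend on the Appendix A label. Section 6.7 says these additional endpoints will not be tested. Renal failure is not in the Section 5.2 list of Major Complications. Creatinine is scheduled at few time points after the procedure, so the criterion has limited scope.

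Three stronger readings are tempting, and the documents do not support them:
- A reader might infer that the whole definition cancels itself. It does not, because the dialysis criterion survives when the rise is 1.0 mg/dL or less.
- A reader might infer that renal harm goes uncounted. It does not; step 3 shows that the cases stay reportable under another label.
- A reader might see a parallel defect in the perforation row, which reads "Defined as perforation in an access vessel wall or the aorta confirmed by extravasations of contrast under fluoroscopy", because Section 8.1 also names "Damage to vessels adjacent to the vessels used for advancing the system". But Section 8.1 lists that injury apart from perforation, so a narrower perforation term contradicts nothing. The bleeding, hematoma, retroperitoneal hemorrhage and general vascular rows can still capture such injuries. The fistula row accepts more ways of confirmation ("as documented by CT, ultrasound, angiography, or direct observation"), but different events may have different confirmation rules, and asking for the same ones is a preference.

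**Conclusion.** The renal failure definition is wrong as written. For every eligible baseline the creatinine criterion is empty on a literal reading, and new dialysis with a rise above 1.0 mg/dL is also excluded. The affected events would be labelled renal insufficiency: misclassification in descriptive tables, without loss from reporting.

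The severity is minor. No effect on the primary safety endpoint, the 16% goal, the stopping rules or the sample size is shown. A renal event could enter that endpoint only through a listed item such as hospitalization, whose Appendix L definition is not available here. The documents give no renal event rates, so the number of mislabelled cases cannot be stated and may be zero.

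The conclusion assumes that the baseline in Appendix A is the value used for eligibility, and that exclusion 18 is observed. A subject enrolled in breach of it, at 2.5 mg/dL or above, could reach 3.5 mg/dL with a rise of 1.0 mg/dL or less.

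**What to change.** Reconcile the two sentences using thresholds already in the protocol. One wording that does so is: *A rise of more than 1.0 mg/dL over baseline that neither reaches 3.5 mg/dL nor leads to new dialysis is not renal failure.* It would help to add that such a rise is recorded under renal insufficiency, since renal dysfunction has no row.

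Then recheck any renal events already coded against the reconciled text. The cost is one sentence in Appendix A and a short review of existing records: Section 1.2 gives 61 single-arm subjects enrolled in its text and 74 in Table 6, out of a maximum of 250. The count under renal failure may rise and the count under renal insufficiency may fall by the same events. No threshold, endpoint or sample size changes, and the perforation row needs no change on this account.

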Appendix B Classes of Anti-Arrhythmic Drugs (Vaughn-Williams Classification)

CLASS IA – Sodium channel block (intermediate association/ disassociation)

Uses: APB and VPB suppression, SVT and VT suppression, AF or atrial flutter, and Ventricular Fibrillation suppression

Disopyramide

Procainamide

Quinidine

CLASS IB – Sodium channel block (fast association/ disassociation)

Uses: Suppression of ventricular tachycardia and atrial fibrillation

Lidocaine

Mexiletine

Phenytoin

Tocainide

CLASS IC

Uses: APB and VPB suppression, SVT and VT suppression, AF or atrial flutter, and ventricular fibrillation suppression

Flecainide

Propafenone

Moricizine

CLASS II - β -Blockers

Uses: Supraventricular tachyarrhythmias (APB, ST, SVT, AF, atrial flutter) and ventricular arrhythmias (often in a suppressive role)

Atenolol

Carvedilol

Acebutolol

Betaxolol

Bisoprolol

Esmolol

Metoprolol

Nadolol

Propranolol

Timolol

CLASS III – Potassium channel blocker

Uses: Any tachyarrhythmia except Torsades' de Pointes ventricular tachycardia

Amiodarone

Azimilide

Bretylum

Dofetilide

Dronedarone

E-4031

Ibutilide

Sotalol

CLASS IV - Calcium channel blockers

Uses: Termination of SVT and slowing of rapid AF or atrial flutter

Diltiazem

Verapamil

Class V

Uses: Suppression of SVT, especially in Heart Failure with AF, contraindicated in ventricular arrhythmias. Magnesium Sulfate used in Torsades' de Pointes

Adenosine

Digoxin

Magnesium Sulfate
